#### **4.3 Inclusion Criteria**

- $\geq 18$  years of age
- Need for elective supratentorial craniotomy
- Preoperative GCS  $> 13$

#### **4.4 Exclusion Criteria**

- Preoperative GCS  $\leq 13$
- Child ( $< 18$  years of age)
- Inability to understand or use the visual analog scale (VAS)
- Proven or suspected allergy to local anesthetics
- Craniotomy incision extending beyond the field of the block
- Patients chronically (more than 2 wk) treated with narcotic medications
- Previous scalp incision
- Bilateral craniotomies
- Allergies to local anesthetics
- GCS verbal score  $< 4$  after extubation
- Patients whose surgeries extend past 6 hours (will be placed on standard of care and removed from study)
- Patients currently on ergot-type oxytotic drugs, MAOIs, or certain antidepressants
- Lactating Mothers

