## Study Summary

|                           |   |
|---------------------------|---|
| Title              | Randomized study of cranial blocks for postoperative anesthesia to reduce pain and postoperative opioid usage  |
| Short Title        | Cranial blocks for postoperative anesthesia   |
| IRB Number         | 834603  |
| Protocol Number    | N/A   |
| Methodology        | Prospective single-blinded randomized controlled trial  |
| Study Duration     | 12 months   |
| Study Center(s)    | Single-center   |
| Objectives         | Primary: 

• To assess the effectiveness of analgesia by scalp nerve block with various agents in the first 72 hours following elective craniotomy.

 |
| Number of Subjects | 90  |

|  |   |
|--|---|
| Main Inclusion and Exclusion Criteria | 
Inclusion Criteria
 
 
• <math>\geq 18</math> years of age
 
• Need for elective supratentorial craniotomy
 
• Preoperative GCS <math>> 13</math>
 
 
Exclusion Criteria
 
 
• Preoperative GCS <math>\leq 13</math>
 
• Child (<math>< 18</math> years of age)
 
• Inability to understand or use the visual analog scale (VAS)
 
• Proven or suspected allergy to local anesthetics
 
• Craniotomy incision extending beyond the field of the block
 
• Patients chronically (more than 2 wk) treated with narcotic medications
 
• Previous scalp incision
 
• Bilateral craniotomies
 
• Allergies to local anesthetics
 
• GCS verbal score <math>< 4</math> after extubation
 
• Patients whose surgeries exceed 6 hrs (will be removed from study and maintained with standard of care)
 
• Patients currently on ergot-type oxytotoxic drugs, MAOIs, or certain antidepressants
 
• Lactating mother
 
 |
| Intervention                          | 
This study compares the standard of care to the standard of care plus the administration of bupivacaine or liposomal bupivacaine in patients receiving craniotomies.
   |
| Statistical Methodology               | 
A Mann-Whitney U test will be used to analyze the primary endpoint of subjects' subjective pain scores. A paired t-test will be used for all secondary endpoints.
  |

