### **3.2 Allocation to Interventional Group**

The Neurosurgery Clinical Research Division (NCRD) will generate a randomization table by computer, which assigns subjects 1:1:1 to the three groups, in random blocks of 3 and 6. On the morning of the procedure, subjects will be assigned sequentially to the lowest unassigned randomization number. The surgeon performing the procedure and operating room staff will not be blinded to the intervention, since they will see whether the patient is receiving liposomal bupivacaine, bupivacaine or saline. However, all providers obtaining post-operative data from the patients will be blinded as to which treatment the patient received, in addition to the patient themselves.

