### **5 Study Procedures**

#### Randomization

The Neurosurgery Clinical Research Division (NCRD) will generate a randomization table by computer, which assigns subjects 1:1:1 to the three groups, in random blocks of 3 and 6. On the morning of the procedure, subjects will be assigned sequentially to the lowest unassigned randomization number.

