### Cranial block administration

The anesthesia protocol will be standardized for all patients. All routine drugs will be administered per standard clinical guidelines as directed by the anesthesiologists. Anesthetic induction and maintenance will be at the discretion of the attending anesthesiologist. Cranial block is performed at the start of the case as standard of care for all craniotomy procedures. Muscle relaxants will be used as needed and reversed at the end of the surgery, based on standard clinical practice.

Per standard of care, after craniotomy, post-operative pain is managed with systemic opiate medications. Certain surgeons in the department (including the PI) perform post-operative cranial blocks to limit post-operative pain and minimize subsequent narcotic use. However, this is not standard of care and is not common practice for many neurosurgeons in the department. Inclusion of a placebo group mirrors the practice of other neurosurgeons within the department who do not perform post-operative blockade unless the operation is long (e.g. >6h). As there is no uniform national standard regarding the use of post-operative local anesthetics, the use of these medications falls within the domain of individual practice patterns. Patients in the placebo arm will share the same risk of postoperative pain as patients in the routine practice of some practitioners.

Under this protocol, the surgeon will administer a cranial block (bupivacaine, liposomal bupivacaine, or placebo), according to a technique previously described by Pinosky et al (Pinosky et al., 1996). The solution for the cranial block will be supplied by the OR pharmacy. The OR nurse will deliver the solution into a sterile container on the sterile field. The solution will be drawn into a syringe for the surgeon to immediately administer. The supraorbital, supratrochlear, zygomaticotemporal, auriculotemporal, postauricular lesser and greater occipital nerve branches on the ipsilateral side of the operation will be blocked with 5-10 cc of solution (with a maximum of 60 cc at all sites) by needle infiltration. This process

generally takes 1-2 minutes. Following this, the general anesthesia is lightened and the patient is extubated in usual fashion.

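### Patients are allocated on the morning of surgery but removed if the operation passes 6 hours; nothing conceals the arm until the block or keeps removed patients in the analysis, so selection bias is possible and could not be detected

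*Combined protocol and SAP*

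**What the plan says.** - **Allocation.** Section 3.2, repeated in section 5 and section 5.2.1 under Randomization: "On the morning of the procedure, subjects will be assigned sequentially to the lowest unassigned randomization number".
- **The 6-hour rule.** It is listed as an exclusion criterion in section 4.4 ("Patients whose surgeries extend past 6 hours (will be placed on standard of care and removed from study") and in the Study Summary ("Patients whose surgeries exceed 6 hrs (will be removed from study and maintained with standard of care").
- **Blinding.** Section 3.2: "The surgeon performing the procedure and operating room staff will not be blinded to the intervention". The reason given is "since they will see whether the patient is receiving liposomal bupivacaine, bupivacaine or saline". Patients and the nurses who rate pain are blinded.
- **Position of the study block.** Sections 5 and 5.2.1, Cranial block administration, describe the injections and continue: "Following this, the general anesthesia is lightened and the patient is extubated in usual fashion". The same subsection also states: "Cranial block is performed at the start of the case as standard of care for all craniotomy procedures".
- **Local practice in long cases.** The same subsection explains the placebo arm by reference to surgeons "who do not perform post-operative blockade unless the operation is long (e.g. >6h".
- **Analysis.** Sections 6.2 and 6.2.2 name tests but no analysis population. Section 6.1 allows 10% for dropout and does not name long operations as a cause.

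The plan does not say who decides that 6 hours have passed, when the clock starts and stops, or whether removed patients are replaced.

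**The concern.** An eligibility criterion should be settled before allocation. This one cannot be, because the length of the operation becomes known only hours after the arm has been assigned. Every patient it removes is therefore a post-randomisation exclusion, and the analysed groups need not be the randomised groups.

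The person whose pace largely sets the operating time is unblinded, and the plan has no step that withholds the morning's allocation from that person until the block is drawn up. Removal may also matter to the patient's care. Since some surgeons give a post-operative block in long cases, leaving the study may change whether a patient assigned saline receives an active block. In a case close to the limit, a surgeon who knew the arm could have an arm-related reason to call it.

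At stake is the comparison of pain scores. The removed operations are the longest, and these may differ in pain, ICU stay and hospital stay. If removal differed by arm, the analysis as planned could neither show it nor correct it.

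**Working it through.** **1. The plan's own figure.** Section 6.1 gives 30, read as per arm because 90/3 = 30, for d = 1.01, alpha 0.05, power 0.8 and 10% dropout. The normal approximation with two-sided alpha gives n = 2(1.960 + 0.842)²/1.01² = 15.4, so 16 per arm (17 with the t distribution). Dividing by 0.90 gives 18 or 19. The stated 30 is not reproduced on these inputs, but it is larger than needed. That is a separate matter and nothing below rests on it.

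**2. Numbers lost and power.** The documents give no share of operations over 6 hours, so the share q is assumed. Patients left per arm are 30(1 − q), and 30(1 − q)(0.90) if the planned 10% dropout occurs as well. Power is for a two-sample t-test, d = 1.01, two-sided 0.05.

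| Assumed q | Left per arm | Power | Left after 10% dropout too | Power |
|---|---|---|---|---|
| 0% | 30 | 97.0% | 27 | 95.4% |
| 10% | 27 | 95.4% | 24.3 | 93.2% |
| 20% | 24 | 92.9% | 21.6 | 90.0% |
| 30% | 21 | 89.1% | 18.9 | 85.6% |

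Power stays above the stated 80% throughout. With random removal of 5% to 20%, simulation of three arms of 30 gives an average gap between largest and smallest arm of 1.9 to 3.7 patients, which is also minor.

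**3. Bias if removal depends on the arm.** Let operating time L be standard normal, let pain have correlation ρ with L, and let there be no treatment effect. Removing the longest fraction p of an arm leaves a mean L of −m(p), where m(p) = φ(z)/(1 − p) and z is the 1 − p quantile.

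- m(0.10) = 0.1755/0.90 = 0.195
- m(0.20) = 0.2800/0.80 = 0.350
- m(0.30) = 0.3477/0.70 = 0.497

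The saline-minus-active shift in pain, in SD units, is −ρ[m(saline) − m(active)].

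| Removed, active vs saline (assumed) | ρ (assumed) | Shift | Simulated type I error |
|---|---|---|---|
| 10% vs 10% | 0.3 or 0.5 | 0 | 4.7% |
| 10% vs 20% | 0.3 | −0.3 × 0.155 = −0.05 | 5.4% |
| 10% vs 20% | 0.5 | −0.5 × 0.155 = −0.08 | 5.9% |
| 10% vs 30% | 0.3 | −0.3 × 0.302 = −0.09 | 6.4% |
| 10% vs 30% | 0.5 | −0.5 × 0.302 = −0.15 | 8.2% |

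The type I errors come from 20,000 simulated trials per row (30 per arm before removal, two-sided t-test), and the simulated shifts agree with the formula. With ρ = 0 there is no shift and the type I error stays at 5.0% to 5.2%. In these scenarios more long cases leave the saline arm, which makes saline look better; removal in the opposite direction reverses the sign.

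**4. Order of events.** Allocation (morning), then the 6-hour mark (during the operation), then the study block (just before anaesthesia is lightened). On this reading the criterion is largely settled before any study drug is given, so nothing in the design requires the arm to be assigned hours earlier.

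**The case against.** The strongest case on the other side has four parts.

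- **The surgeon may not know the arm.** A reader might infer that the limit is called by someone who already knows the allocation. The documents do not say so. Section 3.2 bases the lack of blinding on seeing the agent, and the agent is used at the end of the case. This stands: knowledge at 6 hours is possible, not stated. What remains is that nothing conceals an allocation made that morning.
- **Data may not be lost.** A reader might take removal from the study to mean that no data are kept. No section says that. Section 5 has pain scores entered in the electronic record as in routine care, and section 5.4 provides a final visit for early withdrawals, though without naming 6-hour removals. This stands too. The gap is that no section puts these patients into the analysis.
- **The bias is conditional and modest.** If the block comes at the end, the drug cannot alter operating time. Bias then needs both arm-dependent removal and a link between duration and pain. This stands, and it limits the severity.
- **The trial is not left short of patients.** The 10% allowance in section 6.1 covers surgical revision and other factors, which can be read to include long operations, and power holds in any case. A reading that the rule leaves the trial underpowered is not supported.

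**Conclusion.** The concern holds as a design weakness. The plan allocates patients and later removes some of them on a criterion that only the operation can reveal. It does not conceal the arm in between, and it has no analysis set that keeps those patients. The harm is possible selection bias, not lost power.

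Its size cannot be fixed from the documents. It is nil if removal is equal across arms or if duration is unrelated to pain. Under the assumed unequal rates and correlations above it is 0.05 to 0.15 SD, with type I error of 5.4% to 8.2%. The documents do not show that arm-dependent removal would occur; they show that the plan could not detect it if it did.

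This assumes that the study block is given at the end of the case. If the sentence placing a block at the start of the case refers to the study block, the rule would remove patients who had already been treated, which is worse. The plan should be changed on this point, but it is a should-fix and not a fatal flaw.

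**What to change.** 1. **Allocate later.** In sections 3.2, 5 and 5.2.1, replace the morning-of-surgery wording. The NCRD releases the next assignment as late as practicable, immediately before the study solution is prepared, once the 6-hour criterion has been checked. Patients already over the limit are then screen failures, not randomised dropouts. The 6-hour rule itself is unchanged.
2. **Keep everyone who is allocated.** A case can still pass 6 hours during closure. State in section 6.2 that any patient who passes the limit after allocation stays in follow-up and in the primary analysis by assigned arm, using the VAS, narcotic and length-of-stay data in the electronic record. Report removals by arm.
3. **Define the limit.** State when the 6-hour clock starts and stops and who calls it.
4. **Reconcile related text.** Sections 3.3, 4.4, 5 and 5.2.1 also exclude patients with a GCS verbal score below 4 after extubation. That exclusion arises after the block, so later allocation does not solve it, and it must be reconciled with the analysis rule in step 2. The statements on whether a block is given at the start or the end of the case must be reconciled as well. If the study block were at the start, step 1 could not work and step 2 would have to carry the whole correction.

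**Cost.** The agent must be dispensed and transported during the operation instead of being arranged in the morning; for liposomal bupivacaine this involves the OR pharmacy, transport by the NCRD and dilution on the field. If screen failures are replaced, more patients must be consented: reaching 90 allocated takes 90/0.90 = 100 at an assumed 10% over 6 hours, or 90/0.80 = 112.5, so 113, at 20%. Section 4.2 foresees no additional recruitment and would need to say so. The rest is protocol wording.

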#### **4.5 Subject Recruitment**

We plan to recruit adult patients who are undergoing or preparing to undergo an elective craniotomy for any reason at the Hospital of the University of Pennsylvania (HUP). A craniotomy is a procedure that allows neurosurgeons to access the brain for purposes such as resection of a tumor or clipping of an aneurysm. Patient recruitment will encompass all neurosurgeons practicing at HUP. Informed consent will be obtained from all participants. All consent forms will be retained in a locked file in the NCRD office.

#### **4.6 Vulnerable Populations:**

Children, pregnant women, fetuses, neonates, or prisoners will not be included in this research study.

### **5 Study Procedures**

#### Randomization

The Neurosurgery Clinical Research Division (NCRD) will generate a randomization table by computer, which assigns subjects 1:1:1 to the three groups, in random blocks of 3 and 6. On the morning of the procedure, subjects will be assigned sequentially to the lowest unassigned randomization number.

### Preparation

The anesthesia for each treatment arm will be supplied by the OR pharmacy or the OR Omnicell, as per standard protocol. If the patient is randomized to liposomal bupivacaine (1.33% injection), the OR pharmacy will dispense the medication to the NCRD for transport to the OR for preparation on the field. 20 mL of liposomal bupivacaine will be diluted in 40 mL of sterile, injectable saline (0.9% sodium chloride USP), for a total volume of 60 mL. The surgeon will then draw up the medication for use in a sterile syringe. The patients randomized to bupivacaine (0.25% injection) and placebo (0.9% sodium chloride injection USP) will have the OR nurse obtain the randomized medication from the OR Omnicell per standard practice. 60 mL of the randomized medication will be placed on the sterile field and drawn up into a sterile syringe by the surgeon for use.

### Cranial block administration

The anesthesia protocol will be standardized for all patients. All routine drugs will be administered per standard clinical guidelines as directed by the anesthesiologists. Anesthetic induction and maintenance will be at the discretion of the attending anesthesiologist. Cranial block is performed at the start of the case as standard of care for all craniotomy procedures. Muscle relaxants will be used as needed and reversed at the end of the surgery, based on standard clinical practice.

Per standard of care, after craniotomy, post-operative pain is managed with systemic opiate medications. Certain surgeons in the department (including the PI) perform post-operative cranial blocks to limit post-operative pain and minimize subsequent narcotic use. However, this is not standard of care and is not common practice for many neurosurgeons in the department. Inclusion of a placebo group mirrors the practice of other neurosurgeons within the department who do not perform post-operative blockade unless the operation is long (e.g. >6h). As there is no uniform national standard regarding the use of post-operative local anesthetics, the use of these medications falls within the domain of individual practice patterns. Patients in the placebo arm will share the same risk of postoperative pain as patients in the routine practice of some practitioners.

Under this protocol, the surgeon will administer a cranial block (bupivacaine, liposomal bupivacaine, or placebo), according to a technique previously described by Pinosky et al (Pinosky et al., 1996). The solution for the cranial block will be supplied by the OR pharmacy. The OR nurse will deliver the solution into a sterile container on the sterile field. The solution will be drawn into a syringe for the surgeon to immediately administer. The supraorbital, supratrochlear, zygomaticotemporal, auriculotemporal, postauricular lesser and greater occipital nerve branches on the ipsilateral side of the operation will be blocked with 5-10 cc of solution (with a maximum of 60 cc at all sites) by needle infiltration. This process

generally takes 1-2 minutes. Following this, the general anesthesia is lightened and the patient is extubated in usual fashion.

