#### **5.6 Safety Evaluation**

A local safety officer will have access to unblinded data, including patient identification and drug group. [name], MD, PhD, has extensive experience with randomized controlled studies, and has served in the capacity of Safety Officer for studies. [name], in collaboration with the study coordinator, will review patient data once five subjects have been enrolled. When 15 additional subjects have been enrolled for a total of 20, [name] will again review the data. Reviews will continue at increments of 20 subjects, at enrollment totals of 40 and 60. Specifically, the Safety Officer will independently examine the primary outcome measure (i.e. cumulative pain intensity scores) and secondary outcome measures (i.e. GCS, narcotic utilization, time to rescue medication, ICU length of stay, hospital length of stay), as well as remain vigilant for any adverse events. If any adverse events are suspected, enrollment will immediately cease, the IRB will be notified, and a meeting between the Safety Officer, PI and study coordinator will take place.

[name] contact information will be provided on the study instruction sheet provided to nurses and available in the patient's chart. If any clinical staff suspects an adverse event, the study sheet provides instructions to contact the IRB and [name] immediately. Additional contact information for the PI, and the study coordinator will be listed for any concerns.

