## **7.3 Relationship of AE to Study**

The PI and safety monitor will be jointly making the determination the relationship of each adverse event to the study procedure. Prior studies have described AE's common to this procedure to be nausea, emesis, and hypotension (Brown et al., 2019). These will be considered to be probably or definitely related to the procedure, after analysis of the data is considered. Other AEs will be determined and characterized on a case by case basis.

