The cardiac toxicity profile of liposomal bupivacaine subcutaneous injection both in healthy volunteers and in patients undergoing total knee arthroplasty has also been reviewed (Bergese, Onel, Morren, & Morganroth, 2012; Naseem et al., 2012). Four doses (150, 300, 450, or 600 mg) of liposomal bupivacaine were compared to bupivacaine HCl with epinephrine injected. There were no significant differences in change from baseline in QRS or QTc duration between the two groups, nor did they differ in mean change from baseline heart rate and PR interval. In healthy volunteers receiving 300, 450, 600, and 750 mg subcutaneous injection, none of the participants had a maximum QTc interval greater than 500 ms, and there were no changes in QTc of greater than 60 ms at any measured time point.

[name] will verbally report adverse events of any type in patients enrolled in this study to the University of Pennsylvania IRB and Study Officer within 24 hours of the time of the event. The event will then be documented in detail and submitted in writing within 10 days. Any adverse event that might occur would more likely be related to clinical causes than to this study.

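### All three arms receive a start-of-case cranial block after assignment, and nothing keeps the arm from the unblinded operating team until that block has been given

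*Combined protocol and SAP*

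**What the plan says.** Section 5, Cranial block administration, repeated in section 5.2.1, states: "Cranial block is performed at the start of the case as standard of care for all craniotomy procedures". The same section places the randomized injection at the end of the operation, immediately before anesthesia is lightened. On allocation, section 3.2 says: "On the morning of the procedure, subjects will be assigned sequentially to the lowest unassigned randomization number". On blinding it says: "The surgeon performing the procedure and operating room staff will not be blinded to the intervention", because they will see which solution is used. Patients and the nurses who rate pain are blinded.

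For the randomized solution the plan is specific: each nerve is to be "blocked with 5-10 cc of solution (with a maximum of 60 cc at all sites"). For the start-of-case block, section 5 gives no agent, concentration, volume or dose. It says that anesthesia will be standardized, but leaves routine drugs to clinical guidelines and the anesthesiologists' direction. Section 1.1 names a 1:1 mixture of lidocaine 1% with epinephrine and bupivacaine 0.5%, but as the PI's own routine and without a volume. Section 4.5 recruits from all the hospital's neurosurgeons.

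The outcome lists in section 3.3 and under Postoperative Data Collection do not mention the first block. Section 8.2 has a general item for details of the operation. The Study Summary defines the comparison as standard of care against standard of care plus an active agent.

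**The concern.** The first block is a local anesthetic co-treatment given after randomization. Staff who may already know the arm give it, and the plan does not bind its content. A clinician who knows that a patient will receive saline could block more generously at the start. One who knows that liposomal bupivacaine is coming could block less. Either choice would be reasonable care, but both make the first block depend on the arm. Blinded raters cannot correct for this, because it would change the pain itself and not the rating of it.

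At stake is how the early pain scores are read, chiefly the comparison of plain bupivacaine with saline. Heavier first blocks in saline patients would shrink that difference, and lighter ones would enlarge it. With no pre-specified summary of the first block by arm, a reader of the results could not tell whether this had happened.

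**Working it through.** **1. Order of events.** Assignment on the morning of surgery (section 3.2), then the start-of-case block, surgery, the randomized block, and extubation (section 5). The first block therefore always falls between assignment and study treatment, in all three arms.

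**2. Can the team know the arm by then?** Under Preparation in section 5, the NCRD carries liposomal bupivacaine to the operating room, while the nurse takes plain bupivacaine or saline from the dispensing cabinet. Someone in the room must be told the arm, and the source of the drug differs by arm. No time is given for either step. Early knowledge is possible but not established.

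**3. Could the first block still act when pain is scored?** Residual cover after extubation = max(0, D − S), where D is block duration and S is the time from first block to extubation, taken as the length of surgery. Operations longer than 6 hours leave the study (section 4.4), so S = 2, 4 and 6 hours are used.

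| S | D = 4 h (section 1.1, up to four hours) | D = 6 h (section 6.1, effect said to begin to diminish after this) |
|---|---|---|
| 2 h | 2 h | 4 h |
| 4 h | 0 h | 2 h |
| 6 h | 0 h | 0 h |

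The largest entry is 4 of 72 hours, or 5.6%. It only reaches the start of the 4–6 hour window used for planning. Section 6.1 describes the start of a decline and not an end, so some tail beyond 6 hours cannot be excluded.

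**4. Is the first block large enough to matter?** Assume the section 1.1 mixture, which contains 5/2 = 2.5 mg/mL bupivacaine, at an assumed 10–60 mL. That is 25–150 mg. The plain bupivacaine study dose is at most 60 mL × 2.5 mg/mL = 150 mg. On these assumptions the first block runs from a sixth of the study dose to the same size. This is a comparison of scale only.

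**5. How much dilution could the trial absorb?** Section 6.1 gives 30 for d = 1.01, power 0.8, alpha 0.05 and 10% dropout; 90 patients in three arms implies 30 per arm. The plain two-sided formula, 2(1.960 + 0.842)²/1.01² = 15.4, gives 16 per arm, and 16/0.9 gives 18 (19 from the t-based calculation). The stated 30 is therefore not reproduced this way, but it is larger and this point does not depend on it. With 30 × 0.9 = 27 evaluable per arm, power = Φ(d√(27/2) − 1.96):

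| d (values below 1.01 are assumed) | Power |
|---|---|
| 1.01 | 96% |
| 0.8 | 84% |
| 0.7 | 73% |
| 0.6 | 60% |

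By the t-test, power falls below 80% once d is under about 0.78, which is (1.01 − 0.78)/1.01 = 23% less than planned. Nothing in the documents shows whether dilution would be smaller or larger than that, or whether patients in the study behind d = 1.01 also had a start-of-case block.

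**The case against.** The strongest reply is that a background block common to all arms is a legitimate design. It matches the Study Summary, and when given alike it leaves the randomized comparison unbiased. Section 3.2 explains the unblinding by sight of the study solution, which is used only at the end, so the team may not know the arm at the start. Routine dosing is also governed by clinical guidelines. All of this stands. It makes arm-dependent dosing a possibility and not a finding. But the plan does not state the timing on which this reassurance depends.

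Several stronger readings are tempting, and the documents do not support them.

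- **An unsafe combined dose.** No figure shows a toxic total. Section 1.1 ties systemic toxicity to high-dose intravenous injection. Section 10.1 covers liposomal bupivacaine given alone, up to 750 mg. Adding plain to extended-release milligrams given hours apart does not measure a peak. A mg/kg cap on usual care has no number to rest on and would restrict saline patients too, although section 10.4 says enrolment does not influence clinical care.
- **No timing and no record of the first block.** Section 5 says when it is given; only a clock time or interval is missing. The case report form is not in the documents, and section 8.2 has a general item for the operation.
- **Safety decisions made without the first dose.** Section 7.3 says "The PI and safety monitor will be jointly making the determination the relationship of each adverse event to the study procedure", and section 5.6 says "If any adverse events are suspected, enrollment will immediately cease". Nothing stops those people from consulting the clinical record, and the safety officer has identified, unblinded data. Section 7.3 says of nausea, emesis and hypotension "These will be considered to be probably or definitely related to the procedure", but the sentence goes on to make this depend on the data.

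**Conclusion.** The point holds as a gap in concealment around a post-randomization co-treatment. All arms receive a start-of-case block after assignment, its agent and dose are not bound, and the plan does not withhold the arm from the team until it has been given. Neither bias nor harm is shown.

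Any overlap with the pain scores is early: 0 to 4 hours of 72 on the two durations that the documents give for bupivacaine scalp blocks. It is confined mainly to shorter operations, and the resulting dilution cannot be estimated. The residual-cover figures assume that the first block behaves like plain bupivacaine. The scale comparison assumes the PI's mixture and a volume of 10–60 mL. This is a cheap improvement worth making before enrolment, not a reason to doubt the design.

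**What to change.** In section 3.2 and in section 5 (with its repeat in section 5.2.1), add wording such as: the NCRD keeps the assignment concealed from the surgeon, the anesthesia team and the operating room staff until the start-of-case block has been given, and releases the arm and the study drug only in time for the end-of-case injection. Release should follow the same steps in all three arms, so that an NCRD delivery of liposomal drug does not reveal the arm early.

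As a supporting step, copy the agent, dose and time of the start-of-case block from the anesthesia record and tabulate them by arm. The documents do not describe that record; I assume that it holds these items. Choice of agent and dose stays with the clinical team.

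The cost is that the NCRD must act during the case instead of before it, and three fields per patient must be transcribed (3 × 90 = 270 entries). The team must also choose the first block without knowing whether an active study dose will follow. No extra patients, visits or tests are needed.
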